6.2 Pembrolizumab dosing delays

Participants should be carefully monitored for toxicity. If a treatment delay is required for pembrolizumab, treatment with Eribulin is allowed. Guidelines for dose interruption recommendations for pembrolizumab are shown in Table 4. If treatment with pembrolizumab is withheld permanently, participants are allowed to continue to receive eribulin therapy. Evaluation of possible AEs should occur early, with early withholding of drug, and appropriate treatment as indicated in the management tables and following event specific guidelines. In some cases, pembrolizumab may be resumed as per section 5.9

AEs associated with pembrolizumab exposure may represent an immunologic etiology. These immune-related AEs (irAEs) may occur shortly after the first dose or several months after the last dose of pembrolizumab treatment and may affect more than one body system simultaneously. Therefore, early recognition and initiation of treatment is critical to reduce complications. Based on existing clinical study data, most irAEs were reversible and could be managed with interruptions of pembrolizumab, administration of corticosteroids, and/or other supportive care. For suspected irAEs, ensure adequate evaluation to confirm etiology or exclude other causes. Additional procedures or tests such as bronchoscopy, endoscopy, skin biopsy may be included as part of the evaluation. Based on the severity of irAEs, withhold or permanently discontinue pembrolizumab and administer corticosteroids. Dose interruption and toxicity management guidelines for irAEs associated with pembrolizumab are provided in Table 4.1 to Table 4.9.

Table 4.1 Guidelines for dose interruption and toxicity management guidelines for immune-related AEs associated with pembrolizumab

General instructions: 
 1. Corticosteroid taper should be initiated upon AE improving to Grade 1 or less and continue to taper over at least 4 weeks. 2. For situations where pembrolizumab has been withheld, pembrolizumab can be resumed after AE has been reduced to Grade 1 or 0 and corticosteroid has been tapered. Pembrolizumab should be permanently discontinued if AE does not resolve within 12 weeks of last dose or corticosteroids cannot be reduced to ≤ 10 mg prednisone or equivalent per day within 12 weeks. 3. For severe and life-threatening irAEs, IV corticosteroid should be initiated first followed by oral steroid. Other immunosuppressive treatment should be initiated if irAEs cannot be controlled by corticosteroids. 				
Immune-related AEs	Toxicity grade or conditions (CTCAEv5.0)	Action taken to pembrolizumab	irAE management with corticosteroid and/or other therapies	Monitor and follow-up
Pneumonitis	Grade 2	Withhold	
 • Administer corticosteroids (initial dose of 1-2 mg/kg prednisone or equivalent) followed by taper 	
 • Monitor participants for signs and symptoms of pneumonitis • Evaluate participants with suspected pneumonitis with radiographic imaging and initiate corticosteroid treatment • Add prophylactic antibiotics for opportunistic infections
	Grade 3 or 4, or recurrent Grade 2	Permanently discontinue		
Diarrhea / Colitis	Grade 2 or 3	Withhold	
 • Administer corticosteroids (initial dose of 1-2 mg/kg prednisone or equivalent) followed by taper 	
 • Monitor participants for signs and symptoms of enterocolitis (ie, diarrhea, abdominal pain, blood or mucus in stool with or without fever) and of bowel perforation (ie, peritoneal signs and ileus). • Participants with \geq Grade 2 diarrhea suspecting colitis should consider GI consultation and performing endoscopy to rule out colitis. • Participants with diarrhea/colitis should be advised to drink liberal quantities of clear fluids. If sufficient oral fluid intake is not feasible, fluid and electrolytes should be substituted via IV infusion.
	Grade 4	Permanently discontinue		
AST and ALT elevation or Increased bilirubin	Grade 2	Withhold	
 • Administer corticosteroids (initial dose of 0.5- 1 mg/kg prednisone or equivalent) followed by taper 	
 • Monitor with liver function tests (consider weekly or more frequently until liver enzyme value returned to baseline or is stable)

	Grade 3 or 4	Permanently discontinue	
 Administer corticosteroids (initial dose of 1-2 mg/kg prednisone or equivalent) followed by taper 	
Type 1 diabetes mellitus (T1DM) or Hyperglycemia	Newly onset T1DM or Grade 3 or 4 hyperglycemia associated with evidence of β -cell failure	Withhold	
 Initiate insulin replacement therapy for participants with T1DM Administer anti-hyperglycemic in participants with hyperglycemia 	
 Monitor participants for hyperglycemia or other signs and symptoms of diabetes.
Hypophysitis	Grade 2	Withhold	
 Administer corticosteroids and initiate hormonal replacements as clinically indicated. 	
 Monitor for signs and symptoms of hypophysitis (including hypopituitarism and adrenal insufficiency)
	Grade 3 or 4	Withhold or permanently discontinue ¹		
Hyperthyroidism	Grade 2	Continue	
 Treat with non-selective beta-blockers (eg, propranolol) or thionamides as appropriate 	
 Monitor for signs and symptoms of thyroid disorders.
	Grade 3 or 4	Withhold or permanently discontinue ¹		
Hypothyroidism	Grade 2-4	Continue	
 Initiate thyroid replacement hormones (eg, levothyroxine or liothyronine) per standard of care 	
 Monitor for signs and symptoms of thyroid disorders.
Nephritis and Renal dysfunction	Grade 2	Withhold	
 Administer corticosteroids (prednisone 1-2 mg/kg or equivalent) followed by taper. 	
 Monitor changes of renal function
	Grade 3 or 4	Permanently discontinue		
Myocarditis	Grade 1 or 2	Withhold	
 Based on severity of AE administer corticosteroids 	
 Ensure adequate evaluation to confirm etiology and/or exclude other causes
	Grade 3 or 4	Permanently discontinue		
All other immune-related AEs	Intolerable/persistent Grade 2	Withhold	
 Based on type and severity of AE administer corticosteroids 	
 Ensure adequate evaluation to confirm etiology and/or exclude other causes
	Grade 3	Withhold or discontinue based on the type of event. Events that require discontinuation include and not limited to: Guillain-Barre Syndrome, encephalitis		

	Grade 4 or recurrent Grade 3	Permanently discontinue		
1. Withhold or permanently discontinue pembrolizumab is at the discretion of the investigator or treating physician. NOTE: For participants with Grade 3 or 4 immune-related endocrinopathy where withhold of pembrolizumab is required, pembrolizumab may be resumed when AE resolves to \leq Grade 2 and is controlled with hormonal replacement therapy or achieved metabolic control (in case of T1DM).				

Table 4.2 Pembrolizumab dose delay for non-immunologically mediated adverse events

ALL OTHER EVENTS*	Management/Next Dose for Pembrolizumab
\leq Grade 1	No change in dose
Grade 2	Hold until \leq Grade 1 OR baseline (exceptions as noted below); Evaluate and continue at investigator discretion
Grade 3	Stop pembrolizumab (exceptions as noted below)
Grade 4	Stop pembrolizumab
*Not Pembrolizumab related, or pembrolizumab related non-immunologically mediated Recommended management: As clinically indicated	

- Any grade 2 drug-related uveitis or eye pain or blurred vision that does not respond to topical therapy and does not improve to Grade 1 severity within the re-treatment period OR requires systemic treatment should result in protocol treatment discontinuation.
- Any adverse event, laboratory abnormality, or intercurrent illness which, in the judgment of the investigator, presents a substantial clinical risk to the participant with continued study drug dosing should result in protocol treatment discontinuation.
- Tumor pain or associated tumor flare does not require permanent discontinuation.
- Participants with any grade < 2 laboratory abnormality may continue study treatment at the discretion^[SEP] of the investigator. Any grade 3 or 4 drug-related laboratory abnormality or electrolyte abnormality, that can be managed independently from underlying organ pathology with electrolyte replacement, hormone replacement, insulin, or that does not require treatment **does not** require discontinuation.
- Expected hematologic AEs which are related to eribulin will be managed per eribulin dose modification tables and do not require delay of pembrolizumab, see section 6.1

Table 4.3 Pembrolizumab dose delay for skin rash and oral lesions

Skin Rash and Oral Lesions	Management/Next Dose for Pembrolizumab
\leq Grade 1	No change in dose; * evaluate and continue at investigator discretion
Grade 2	Hold* until \leq Grade 1 or resolved. Evaluate and continue at investigator discretion

Grade 3	Hold* until \leq Grade 1; Evaluate and resume at investigator discretion at same dose level
Grade 4	Stop pembrolizumab.
*Participants with purpuric or bullous lesions must be evaluated for vasculitis, Steven-Johnson syndrome, TEN, and autoimmune bullous disease including oral lesions of bullous pemphigus/pemphigoid. Pruritus may occur with or without skin rash and should be treated symptomatically if there is no associated liver or GI toxicity. Note skin rash typically occurs early and may be followed by additional events particularly during steroids tapering.	

Table 4.4 Pembrolizumab dose delay for pancreatitis

Pancreatitis Amylase/Lipase	Management/Next Dose for Pembrolizumab
\leq Grade 1	Continue treatment at same level at investigator discretion.
Grade 2	Continue treatment at same level at investigator discretion if asymptomatic.
Grade 3	Hold until Grade < 2 . Resume at same dose level if asymptomatic. Participants who develop symptomatic pancreatitis or DM should stop pembrolizumab. .
Grade 4	Hold until Grade < 2 . Resume at same dose level if asymptomatic. Participants who develop symptomatic pancreatitis or DM should stop pembrolizumab. .
Participants may develop symptomatic and radiologic evidence of pancreatitis as well as DM and DKA. Lipase elevation may occur during the period of steroid withdrawal and with other immune mediated events or associated with colitis, hepatitis, and participants who have asymptomatic lipase elevation typically have self-limited course and may be retreated. For treatment management of symptomatic pancreatitis please follow the Hepatic Adverse Event Management Algorithm.	

Table 4.5 Pembrolizumab dose delay for nausea and vomiting

Other GI Nausea, Vomiting	Management/Next Dose for Pembrolizumab
\leq Grade 1	No change in dose.
Grade 2	Hold pending evaluation for gastritis duodenitis and other immune adverse events or other causes. Resume at investigator discretion.
Grade 3	Hold pending evaluation until \leq Grade 2. Resume at same dose level. If symptoms do not resolve within 7 days with symptomatic treatment participants should stop pembrolizumab.
Grade 4	Stop pembrolizumab
Participants with grade 2 or 3 N-V should be evaluated for upper GI inflammation and other immune related events.	

Table 4.6 Pembrolizumab dose delay for fatigue

Fatigue	Management/Next Dose for Pembrolizumab
≤ Grade 1	No change in dose.
Grade 2	No change in dose.
Grade 3	Hold until ≤ Grade 2. Resume at same dose level at investigator discretion.
Grade 4	Stop pembrolizumab
Fatigue is the most common adverse event associated with immune checkpoint therapy. Grade 2 or greater fatigue should be evaluated for associated or underlying organ involvement including pituitary, thyroid, and hepatic, or muscle (CPK) inflammation	

Table 4.7 Pembrolizumab dose delay for neurological events

Neurologic events*	Management/Next Dose for Pembrolizumab
≤ Grade 1	Hold dose pending evaluation and observation. Resume with no change in dose when resolved to baseline at investigator discretion
Grade 2	Hold dose pending evaluation and observation. Hold until ≤ Grade 1. Stop pembrolizumab if treatment with steroids is required. Resume at same dose level for peripheral isolated n. VII (Bell's palsy)
Grade 3	Stop pembrolizumab
Grade 4	Stop Pembrolizumab
*Participants with any CNS events including aseptic meningitis, encephalitis, symptomatic hypophysitis, or myopathy, peripheral demyelinating neuropathy, cranial neuropathy (other than peripheral n. VII), GB syndrome, myasthenia gravis should be off study.	

Table 4.8 Pembrolizumab dose delay for infusion reactions

NCI CTCAE Grade	Treatment	Premedication at Subsequent Dosing
Grade 1 Mild reaction; infusion interruption not indicated; intervention not indicated	Increase monitoring of vital signs as medically indicated until the participant is deemed medically stable in the opinion of the investigator.	None
Grade 2 Requires therapy or infusion interruption but responds promptly to symptomatic treatment (e.g., antihistamines, NSAIDs, narcotics, IV fluids); prophylactic medications indicated for ≤24 hrs	
Stop Infusion. Additional appropriate medical therapy may include but is not limited to: IV fluids Antihistamines NSAIDs Acetaminophen Narcotics Increase monitoring of vital signs as medically indicated until the participant is deemed medically stable in the opinion of the investigator. If symptoms resolve within 1 hour of stopping drug infusion, the infusion may be restarted at 50% of the original infusion rate (e.g. from 100 mL/hr to 50 mL/hr). Otherwise dosing will be held until symptoms resolve and the participant should be premedicated for the next scheduled dose. Participants who develop Grade 2 toxicity despite adequate premedication should be permanently discontinued from further study drug treatment
	Participant may be premedicated 1.5h (± 30 minutes) prior to infusion of _____ with: Diphenhydramine 50 mg po (or equivalent dose of antihistamine). Acetaminophen 500-1000 mg po (or equivalent dose of analgesic).
Grades 3 or 4 Grade 3: Prolonged (i.e., not rapidly responsive to symptomatic medication and/or brief interruption of infusion); recurrence of symptoms following initial improvement; hospitalization indicated for other clinical sequelae (e.g., renal impairment, pulmonary infiltrates) Grade 4: Life-threatening; pressor or ventilatory support indicated	
Stop Infusion. Additional appropriate medical therapy may include but is not limited to: Epinephrine** IV fluids Antihistamines NSAIDs Acetaminophen Narcotics Oxygen Pressors Corticosteroids Increase monitoring of vital signs as medically indicated until the participant is deemed medically stable in the opinion of the investigator. Hospitalization may be indicated. **In cases of anaphylaxis, epinephrine should be used immediately. Participant is permanently discontinued from further study drug treatment.
	No subsequent dosing

Appropriate resuscitation equipment should be available at the bedside and a physician readily available during the period of drug administration. For further information, please refer to the Common Terminology Criteria for Adverse Events v5.0 (CTCAE) at http://ctep.cancer.gov
		

Table 4.9 Pembrolizumab dose delay for fever

Fever	Management/Next Dose for Pembrolizumab
≤ Grade 1	Evaluate and continue at same dose level
Grade 2	Continue at investigator discretion
Grade 3	Hold until ≤ Grade 1. Resume at same dose level at investigator discretion.
Grade 4	Stop pembrolizumab
Participants with fever should be evaluated as clinically appropriate. Participants may experience isolated fever during infusion reactions or up to several days after infusion. Evaluation over the course of 1-2 weeks should be done for other autoimmune events that may present as fever	
See section 5.10: Treatment of Pembrolizumab Infusion reactions	

If treatment is delayed >8 weeks for an adverse event, the participant must be permanently discontinued from study therapy.

Participants requiring high dose steroid treatment for autoimmune or inflammatory events should be managed as described in section 5.9, except for a short course of tapering steroids for infusion reaction, skin rash, or endocrine events.

Participants with grade 3 thyroiditis and skin rash may continue therapy as for grade 2 events with resolution and stable replacement treatment.

Participants with thyroiditis or hypopituitarism who are stable as above may be restarted with replacement hormones including thyroid hormone and physiologic doses of corticosteroids. Please note that grade for hypophysitis with symptoms of headache, visual, or neurologic changes or radiologic evidence of pituitary enlargement and other CNS events such as aseptic meningitis or encephalitis should be considered grade 3 events.

Any participant who requires additional immune suppressive treatment beyond steroids should stop pembrolizumab.

Participants requiring > two dose delays, other than for evaluation for the same event, should stop pembrolizumab. Participants may be dose-delayed for evaluation and restarted depending on results.

Prior to starting corticosteroids or hormone replacement for any reason, appropriate endocrine testing including cortisol, ACTH, TSH and T4 must be obtained to document baseline.

Please note that in some cases the treatment algorithms recommend steroids if symptoms do not resolve in 7 days. However, this recommendation is not meant to delay steroid treatment at any time it is clinically indicated.

Any participant started on corticosteroids initially who is determined to not require steroids treatment for an autoimmune adverse event may resume therapy after a 2-week observation period without further symptoms at the discretion of the PI or investigator.

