5.8 Criteria to Resume Treatment after a pembrolizumab related iAE

Management of adverse events is summarized in section 6 and may include holding of pembrolizumab, and/or the use of steroids for the management of immune related AEs. If pembrolizumab is held for toxicity, participants are permitted to continue protocol therapy with eribulin. Eribulin can be continued during corticosteroid treatment.

If drug administration is held until the next scheduled time point, please continue to count weeks/doses. If participants must be delayed due to toxicity, all assessments can be obtained with the modified treatment dose schedule as noted in this section.

Pembrolizumab may be interrupted for situations other than treatment-related AEs such as medical / surgical events or logistical reasons not related to study therapy. Participants should be placed back on study therapy within 8 weeks of the scheduled interruption, unless otherwise discussed with the Sponsor. The reason for interruption should be documented in the participant's study record.

Restarting pembrolizumab may be considered in participants who experience grade 2 events and some grade 3 events (skin rash and thyroiditis). Because of this, stopping treatment and starting steroids earlier, as per section 6, to obtain resolution with the possibility for restarting rather than waiting for higher grade events is encouraged.

For non-autoimmune or non-inflammatory events, participants may resume treatment with study drug when the drug-related AE(s) resolves to Grade ≤ 1 or the baseline value, with the following exceptions:

- Evaluation to exclude any additional immune mediated events (endocrine, GI, and liver / pancreas function) as clinically indicated must be made prior to restarting. [SEP]
- Non-drug-related toxicity including hepatic, pulmonary toxicity, diarrhea, or colitis, must have resolved to baseline before treatment is resumed. [SEP] If the criteria to resume treatment are met, the participant should restart treatment no sooner than the next scheduled time point per protocol. However, if the treatment is delayed past the next scheduled time point per protocol, the treatment should resume at the earliest convenient point [SEP] that is within the five-week delay period.

For participants treated with corticosteroids:

For participants treated with high dose steroids with pembrolizumab, toxicity must resolve to baseline within 8 weeks of treatment.

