Participants should be off steroids for at least 2 weeks with no recurrence or new events. New immune related events or exacerbation of existing events during steroid treatment or taper suggest the presence of ongoing immune activation and should require permanent discontinuation of pembrolizumab.

Grade 2 events must resolve to grade < 1 or baseline before considering retreatment.

All participants treated with steroids for grade ≥ 2 events should have pembrolizumab held until resolution to grade < 1 for at least 2 weeks following complete removal from steroid treatment except for maintenance replacement doses for adrenal insufficiency (preferably no greater than 10mg prednisone equivalent daily).

All participants treated with steroids for grade ≥ 3 events should have pembrolizumab discontinued. Participants with grade 3 thyroiditis and skin rash may continue therapy as for grade 2 events with resolution and stable replacement treatment.

Participants with hepatitis, pancreatitis, pneumonitis, and colitis are at risk for exacerbation with retreatment if there is residual inflammation and should resolve to Grade 0 or baseline before retreatment. Baseline can mean the initial grade *i.e.* grade ≤ 1 where permitted on study.

Participants with thyroiditis or hypopituitarism who are stable as above may be restarted with replacement hormones including thyroid hormone and physiologic doses only of corticosteroids. Please note that hypophysitis with symptoms of headache, visual or neurologic changes or radiologic evidence of pituitary enlargement and other CNS events such as aseptic meningitis or encephalitis should be considered grade 3 events.

Prior to starting corticosteroids or hormone replacement for any reason, appropriate endocrine testing including cortisol, ACTH, TSH and T4 must be drawn if clinically feasible to document baseline function and distinguish the pituitary from peripheral organ dysfunction and later from steroid (or thyroid) treatment associated ACTH (or TSH) suppression. Steroids should be started prior to obtaining results based on clinical indications.

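### Table 4.1 allows pembrolizumab to restart earlier, and at a higher residual grade, than Section 5.8 does; the pointers to Section 5.8 are wrong, and the myocarditis row overlaps the general restart level

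*Combined protocol and SAP*

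**What the plan says.** **Table 4.1 (Section 6.2).** General instruction 1 starts the steroid taper once the event is at Grade 1 or lower and runs it for at least 4 weeks. Instruction 2 then says that "pembrolizumab can be resumed after AE has been reduced to Grade 1 or 0 and corticosteroid has been tapered". It stops the drug for good if the event has not resolved within 12 weeks of the last dose, or if "corticosteroids cannot be reduced to ≤ 10 mg prednisone or equivalent per day within 12 weeks". The only stated exception to the restart level is the note on Grade 3 or 4 endocrinopathy, where restart is possible once the event is at Grade 2 or lower "and is controlled with hormonal replacement therapy or achieved metabolic control".

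The myocarditis row withholds at Grade 1 or 2 and discontinues at Grade 3 or 4. On steroids it says only "Based on severity of AE administer corticosteroids".

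**Section 5.8, for participants treated with corticosteroids.**
- Time off steroids: "Participants should be off steroids for at least 2 weeks with no recurrence or new events".
- Grade: "Grade 2 events must resolve to grade < 1 or baseline before considering retreatment".
- Steroid-treated events of Grade 2 or higher: pembrolizumab is to be "held until resolution to grade < 1 for at least 2 weeks following complete removal from steroid treatment", apart from replacement doses for adrenal insufficiency.
- After high doses: "For participants treated with high dose steroids with pembrolizumab, toxicity must resolve to baseline within 8 weeks of treatment".
- Hepatitis, pancreatitis, pneumonitis and colitis must reach Grade 0 or baseline. Myocarditis is not on that list.

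**Pointers.** The opening of Section 6, the first paragraph of Section 6.2 and the text after Table 4.9 send the reader to Section 5.9 for resumption or steroid management. Section 5.9 is about infusion reactions.

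**The concern.** Two rules in force govern when a participant may again receive the drug that caused an immune event, and they give different answers. The looser one stands in the table an investigator will have open when managing the event. The stricter one stands in a section that the dosing chapter cites under the wrong number. An investigator who follows Table 4.1 as written can restart sooner, and with more residual toxicity, than Section 5.8 allows.

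Myocarditis makes the grade problem visible. Every other organ-specific row of Table 4.1 that withholds by grade does so from Grade 2 or higher, so Grade 1 is a coherent restart level for those rows. The myocarditis row treats Grade 1 as a reason to withhold, yet the same general restart level applies to it.

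What is at stake is participant safety and consistent dose management, not the efficacy analysis.

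**Working it through.** No published figure or statistical calculation is involved. The check sets the rules side by side, with one piece of arithmetic on timing.

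**1. Earliest restart after steroids, counted from the start of the taper**

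Earliest restart = minimum taper + required steroid-free interval.

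| Rule | Minimum taper (instruction 1) | Steroid-free interval | Earliest restart |
|---|---|---|---|
| Table 4.1, instruction 2 | 4 weeks | none stated (0) | 4 + 0 = 4 weeks |
| Section 5.8 | 4 weeks | 2 weeks | 4 + 2 = 6 weeks |

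The difference is 6 − 4 = 2 weeks. It assumes that tapered means the taper is complete. If it means reduced to a low dose that continues, the 2-week clock of Section 5.8 has not yet started, and the difference is larger.

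Section 5.5 supports the 6-week sequence. For high-dose steroids it describes a taper over one month, a two-week observation period and two further weeks to restart. With a month taken as 4 weeks, 4 + 2 + 2 = 8 weeks, which is the maximum interruption stated there.

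**2. Restart grade for a steroid-treated Grade 2 event**

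- Table 4.1: Grade 1 or 0.
- Section 5.8 as printed: below Grade 1, or baseline.
- Section 5.8 if at most Grade 1 was meant: the same level as Table 4.1.

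The text points both ways. The separate Grade 0-or-baseline list would add little if every Grade 2 event already had to fall below Grade 1. On the other hand, the same section prints the at-most sign elsewhere, so the below sign may be deliberate. The timing difference in step 1 does not depend on the answer.

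**3. Myocarditis, case by case**

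| Case | Table 4.1 | Section 5.8 as printed | Restart at residual Grade 1? |
|---|---|---|---|
| Grade 1 onset | Must be reduced, which implies Grade 0 | No explicit grade rule if no steroids were given | No, on the natural reading |
| Grade 2, any steroids | Grade 1 or 0 after taper | Below Grade 1 or baseline, 2 weeks off steroids | Closed, unless Grade 1 was baseline |
| Grade 2, high-dose steroids | Grade 1 or 0 after taper | Baseline within 8 weeks | Closed, unless Grade 1 was baseline |
| Grade 2, no steroids | Grade 1 or 0 | Grade rules stand under the steroid-treated subheading | Open |

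If at most Grade 1 was meant in Section 5.8, the second row also opens for steroid doses that are not high. The documents do not define a high dose, the myocarditis row gives no dose, and the title of Appendix B lists no cardiac algorithm.

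**4. Cross-references**

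| Place | Names | Content is in |
|---|---|---|
| Section 6, opening text (resumption) | 5.9 | 5.8 |
| Section 6.2, first paragraph (resumption) | 5.9 | 5.8 |
| Text after Table 4.9 (high-dose steroids) | 5.9 | 5.8 |
| Table 4.9, last row (infusion reactions) | 5.10 | 5.9 |

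All four are one section too high. Section 5.3.2 cites 5.9 correctly for infusion reactions.

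**The case against.** The strongest reply is that Section 5.8 already protects the participant. An investigator who follows it satisfies both rules, and as printed it bars a Grade 1 restart after any steroids for a Grade 2 event, not only after high doses. That stands, and it narrows the myocarditis gap to the untreated Grade 2 case. It would close even that case if the Grade 2 sentence were read apart from its subheading. It does not settle which rule governs, because the table states no dependence on Section 5.8 and the pointers lead elsewhere.

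Other replies carry some weight:

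- Restart is permitted, never required, and investigators must stop treatment for any event they judge a substantial clinical risk. This makes a bad restart less likely but does not reconcile the rules.
- A hold grade and a restart grade can coincide by design. Table 4.7 does this for neurologic events, although at Grade 2 it stops pembrolizumab if steroids are needed.
- The 10 mg clause in instruction 2 triggers discontinuation and does not grant permission to restart on steroids. Agreed, but even a completed taper leaves no steroid-free interval.
- The pointer slip is editorial, and Section 5.8 sits directly before 5.9. Agreed; it matters because it hides the stricter rule.
- Grade 0 for myocarditis is a clinical judgement that the documents do not impose. Also true. It is proposed because the rationale given for the four listed events, residual inflammation, fits myocarditis as well.

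Three stronger readings are tempting and not supported. A reader might infer that Grade 1 myocarditis meets the restart condition on the day it is withheld; the requirement that the event be reduced rules that out. A reader might set the 6-week restart against the 5-week interruption limit in Section 5.5 and conclude that no restart is possible. That depends on when the first dose is missed and on applying the limit to a pembrolizumab-only hold while eribulin continues, and the text after Table 4.9 gives 8 weeks for an adverse event. Finally, a reader might want an expected number of affected participants. The documents give no myocarditis rate, so any figure would be assumed.

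**Conclusion.** The point holds as a conflict between two safety rules in force, made worse by wrong cross-references. After steroids, Table 4.1 permits restart from 4 weeks after the start of the taper and Section 5.8 from 6, a difference of at least 2 weeks. This assumes the minimum taper of instruction 1 and applies to steroid-treated immune events generally, outside physiologic replacement. The restart grade also differs if Section 5.8 means what it prints.

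The myocarditis overlap is real but narrow. As printed, it leaves a Grade 1 restart open mainly for a Grade 2 case that improves without steroids. It would be wider if at most Grade 1 was intended in Section 5.8.

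The change is worth making because it is cheap and concerns re-exposure after immune toxicity. The primary endpoint, power and type I error are untouched.

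**What to change.** 1. In instruction 2 of Table 4.1, add that after steroids a restart also requires at least 2 weeks off them under Section 5.8, except for physiologic replacement.
2. In the myocarditis row, add that pembrolizumab resumes only at Grade 0 or baseline, and add myocarditis to the Grade 0-or-baseline list in Section 5.8.
3. Confirm whether Section 5.8 means below Grade 1 or at most Grade 1, and print the intended sign in both sentences.
4. Change 5.9 to 5.8 in the opening of Section 6, in Section 6.2 and in the text after Table 4.9. Change 5.10 to 5.9 in Table 4.9.

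The existing interruption and discontinuation limits can stay as they are. The cost is a few lines of text and four corrected numbers, with no added procedure. The downside is a slightly longer hold, or fewer restarts, in rare events.
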